## VI. Statistical Protocol:

**Data Summary.** Descriptive statistics, including graphical displays, will be used to summarize all study variables, both overall and by intervention group. Evidence of imbalance in baseline characteristics will be noted and discussed as to whether they are clinically significant. As recommended by Committee for Proprietary Medicinal Products (CPMP) guidelines, we will consider sensitivity analyses adjusting for these baseline characteristics to ensure that an observed intervention effect is not due to this baseline imbalance. We will construct individual and mean trajectory plots of the longitudinal outcome variables (e.g., BPI) to understand their general trends over the study period. In addition, we will explore the variability and correlation structure of the longitudinal outcome variables. All statistical analyses will be performed using the SAS software package; the VACHS Center of Innovation maintains the current SAS release on our system.

**Intent-to-Treat Analysis.** All primary and secondary analyses focus on the effect of SMK-CBI as compared to SMK-STD. We, therefore, plan to use the intent-to-treat assumption for all analyses; participants will be analyzed as part of the group to which they are randomized, regardless of intervention adherence.

### **Analyses**

**Hypothesis 1.1:** Prolonged abstinence rates will be significantly higher among Veterans in the SMK-CBI group compared to those in the SMK-STD group.

**Hypothesis 1.2:** The 7-day point prevalence abstinence rates will be significantly higher among Veterans in the SMK-CBI group compared to those in the SMK-STD group.

Rates of cigarette abstinence (prolonged abstinence) will be assessed at 6- and 12-month follow-up. Abstinence will be measured as a dichotomous variable that indicates whether patients have been abstinent or not. The same analysis approach will be used to test both prolonged and 7-day point prevalence abstinence rates. Self-report of abstinence will be validated with cotinine saliva testing.

We will use logistic regression to test for a between-group difference in abstinence rates at 6 months. This logistic regression model can be written as:  $\text{Logit}(\pi_i) = \beta_0 + \text{SMK-CBI}_i * \beta_1$ , where  $\pi_i$  represents the probability that patient  $i$  has abstained from smoking at the 6-month follow-up. In this model, SMK-CBI $_i$  is the intervention group indicator; therefore,  $\beta_1$  represents the log-odds ratio of smoking abstinence in the SMK-CBI group as compared to the SMK-STD group. For each of the abstinence outcomes, we will formally evaluate the intervention effect by testing that  $\beta_1$  differs from zero and report the odds ratio ( $\exp(\beta_1)$ ) and 95% CI of the odds ratio. An odds ratio significantly greater than 1.0 provides evidence that SMK-CBI group patients have higher prolonged abstinence rates. The model will also include stratification variables (gender) as recommended in the CPMP guidelines.

Sustainability, or longer term effects of the intervention, will be examined by comparing abstinence rates between groups at 12 months. We will model change in abstinence rates at baseline, 6, and 12 months using generalized linear models with a logit link fit with generalized estimating equations. The regression coefficients from this model have essentially the same interpretation as those from a cross-sectional regression analysis (e.g. logistic regression) but are more appropriate as they properly incorporate the within-subject correlation that is inherent in the longitudinal structure of the data. The model will be fit using the SAS procedure GENMOD (SAS Institute, Cary, NC).

**Hypothesis 2.1:** Veterans in the SMK-CBI will report significantly lower usual pain intensity and pain interference compared to the SMK-STD group.

We will use linear mixed effects models procedure for analyzing repeated measures data with fixed and random effects to evaluate study group assignment effects on our continuous and repeated outcomes (pain intensity and pain interference). The Mixed Models procedure is designed for unbalanced repeated measures with missing data, allowing for intra-participant serial correlation and unequal variance and covariance structure across time. It provides tests of the overall between-participant effects, repeated measures (time) effects, tests of fixed and random effects, and analysis of reduced models that can provide detailed tests of specific pattern of results. A repeated measures analysis of variance in the Mixed Models procedure takes into consideration differences that may emerge over time; we will use this procedure to test for a significant effect of the two treatments on the primary outcome measure, time, and the interactions between time and each of the two treatments. Random effects will also be included to account for intra-participant correlation of repeated measures. Additionally, the model will include the stratification variables. We plan to estimate the parameters in the model using the SAS procedure MIXED (SAS Version 9.2, Cary, NC).

**Hypothesis 3.1:** The relationship between pain-related anxiety intervention and smoking cessation will be mediated by self-efficacy and pain-related anxiety.

If there is a significant intervention effect on smoking cessation (i.e., if  $\beta_1$  is significantly different from zero in the first model above in Hypothesis 1.1), then we also plan to examine whether change in self-efficacy and pain-related anxiety mediate the impact of the intervention. This aim can be addressed under the general framework of mediation. We propose to conduct this mediation analysis using the MacArthur approach, a modification of the traditional Baron & Kenny criteria, developed for use specifically in randomized clinical trials. By the MacArthur definition, the potential mediator must be evident during or post-treatment; therefore, for example, the change in patient self-efficacy measures between baseline and 6-months will be considered as potential mediators. The outcome will be patients' abstinence at 12-months. We will first fit a model to examine the correlation between the mediator (C) and the SMK-CBI group:  $C = \gamma_0 + \gamma_1 * \text{SMK-CBI}$ . We also fit a model that examines the relationship between the mediator and the probability of abstinence (p):  $\text{logit}(p) = \beta_0 + \text{SMK-CBI} * \beta_1 + C * \beta_2 + C * \text{SMK-CBI} * \beta_3$ . Improvements in patient self-efficacy or pain-related anxiety will be considered to account for improvements in abstinence rates if there is evidence that  $\gamma_1$  is not equal to zero, and if either  $\beta_2$  or  $\beta_3$  are not equal to zero.

**E.12.4. Missing Data.** Because the main predictors of interest are collected at baseline, we do not anticipate much missing data in these variables. We do, however, anticipate missing values in the longitudinal outcomes owing to dropout, death, an inability to reach the patient by phone, or item non-response. If the missing values are related to other measured patient factors, such as age, gender, or employment status, then multiple imputation (MI) provides a framework for incorporating information from these auxiliary variables while still preserving a parsimonious main treatment effect model: this framework is described as a significant advantage in recommendations from the Panel on Handling Missing Data in Clinical Trials. We will follow multiple imputation methods presented in Hedeker et al for missing abstinence outcomes. Depending on the type and scope of missing data for other longitudinal variables, MI will be conducted via the SAS procedure PROC MI or the SAS macro IVEware (<http://www.isr.umich.edu/src/smp/ive/>).

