**6. Research Plan:**

**Study methods with proactive recruitment:** Potentially eligible patients will be identified by administrative data pull of pain scores equal to or greater than 4 and current tobacco use. We will oversample women Veterans to increase the diversity. Eligible patients will be sent the following components: Introductory letter: A letter from [name] to introduce the study, make an appeal to the patient to quit smoking, and informs them that they will be called to complete a telephone survey unless they call a toll-free number to refuse participation; Informational Consent Document: A document providing all the information for informed consent into the study and will be sent along with introductory letter and that describes the study.

**Other recruitment methods:** Recruitment will also occur via flyers posted in patient care areas, referrals by providers, and self-referrals from Clinicaltrials.gov at VACHS and VA Central Western Massachusetts Healthcare System (VACWM), and with the monthly pain recruitment table at West Haven and Newington. The anticipated goal for this VACHS study is to recruit 371 veterans, and VACWM will look to recruit 100 Veterans.

Approximately seven days after the mailing, Veterans who have not opted out will receive a phone call from a research assistant (RA) to further assess inclusion criteria, obtain informed consent (if interested), and conduct the baseline survey. Eligible patients must be Veterans enrolled at VACHS or VACWM with current tobacco use, willingness to make a quit attempt in the next 30 days, significant pain defined as  $\geq 4$  on the pain intensity portion of the BPI, and report that their current pain has been present for 3 months or more. Veterans with any of the following will be excluded: active diagnosis of psychosis or dementia in their medical records, Non-english speaking, refusal to provide informed consent, severely impaired hearing or speech, lack of telephone access, enrollment in another research study that might affect the main outcomes of this study, or terminal illness. Participants enrolled into PASS will have a research alert noted in their medical record.

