**Standard of Care:**

At VA specialty-based smoking clinics, counseling sessions with NRT are standard care for assisting Veterans to quit smoking. At the first telephone counseling session, counselors will ask potential participants if they are interested in using NRT. [name] will contact the patient's PCP to facilitate a NRT prescription if the PCP agrees for those participants who are interested in using NRT.

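### Two health systems enrol, but site is in no model: pre-specifying it beside gender is a near-free improvement, worth a little power and not the correction of a bias

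*Combined protocol and SAP*

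**What the plan says.** **Sites.** The Research Plan (section 6) defines the source population by two systems: "Eligible patients must be Veterans enrolled at VACHS or VACWM with current tobacco use". The targets follow under other recruitment methods: "The anticipated goal for this VACHS study is to recruit 371 veterans, and VACWM will look to recruit 100 Veterans".

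**Abstinence models.** Under Analyses, Hypotheses 1.1 and 1.2, the written logistic model has an intercept and a treatment indicator. The plan then adds: "The model will also include stratification variables (gender) as recommended in the CPMP guidelines". The GEE paragraph that follows, for 12-month sustainability, names no covariates.

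**Pain model.** Hypothesis 2.1 says that the mixed model will include the stratification variables, in the plural and without naming them.

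**Mediation models.** Hypothesis 3.1 contains only treatment and mediator terms.

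**Baseline imbalance.** The Data Summary paragraph says that imbalances will be noted and discussed, and that adjusted sensitivity analyses will be considered. Site is not mentioned.

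**Shared delivery.** The Research Plan has one counselor for both sites, and counseling and surveys are by telephone.

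**The concern.** Site is known for every Veteran before randomisation. It could be related to abstinence, to pain, or to whether an abstinence report gets verified, because saliva is collected at a clinic visit. It is the most obvious structural feature of the sample, yet gender is the only stratification variable named and site appears in no model.

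Two things are at stake, both small. First, the share of VACWM participants can differ between arms by chance, and the primary odds ratio is then read without allowance for that. Second, if site predicts abstinence, leaving it out gives up some power. There is also a question of discipline. Adjustment for site could enter only as a sensitivity analysis chosen after imbalance has been inspected, although it could be fixed in advance at almost no cost.

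**Working it through.** The documents give no power, abstinence rates, effect size or dropout, so there is no planned figure to reproduce. The check asks how large the consequence of omitting site could be.

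**Inputs from the documents:** 371 and 100 (Research Plan), and a 95% confidence interval for the odds ratio (Analyses), from which a two-sided 0.05 test is inferred.

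**Assumptions:** 1:1 allocation not stratified by site; targets additive, so N = 371 + 100 = 471, with N = 371 in total as the alternative; site differences in abstinence of 5, 10 and 15 points.

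**Step 1: chance imbalance.** With VACWM share q, the standard deviation of the between-arm difference in share is √[q(1 − q) × 4/(N − 1)].

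- N = 471: q = 100/471 = 0.212; √(0.212 × 0.788 × 4/470) = 0.0377. The 95% range is ±1.96 × 3.77 = ±7.4 points.
- N = 371: q = 100/371 = 0.270; √(0.270 × 0.730 × 4/370) = 0.0461. The 95% range is ±9.0 points.

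**Step 2: resulting shift in the abstinence difference.** Multiply the 95% range by the assumed site difference.

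| Site difference (assumed) | Shift, N = 471 | Shift, N = 371 |
|---|---|---|
| 5 points | ±0.37 points | ±0.45 points |
| 10 points | ±0.74 points | ±0.90 points |
| 15 points | ±1.11 points | ±1.36 points |

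For scale, the sampling standard error of the abstinence difference at N = 471 is √(0.10 × 0.90 × 4/471) = 2.8 points at 10% abstinence and √(0.20 × 0.80 × 4/471) = 3.7 points at 20%. The 95% limit of the shift is well inside one standard error.

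**Step 3: effect on the test.** The logistic model was fitted with and without a site term to the same simulated trials. There were 4,000 runs per setting, with N = 471, 100 at VACWM, unstratified allocation, and 10% control abstinence at the larger site (assumed).

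| Site difference | Null rejection, no site | Null rejection, site | Power at OR 2, no site | Power at OR 2, site |
|---|---|---|---|---|
| 5 points | 4.6% | 4.8% | 74.8% | 75.4% |
| 10 points | 4.9% | 4.9% | 78.4% | 79.0% |
| 15 points | 4.7% | 4.9% | 76.7% | 78.6% |

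The type I error rate is close to 5% with or without site. Power rises by about 0.6 to 2 points when site is added.

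**Step 4: what the odds ratio means.** The simulated log odds ratio within site was ln 2 = 0.693. At a 15-point site difference, the mean estimate was 0.670 without site and 0.699 with it. The first is an average over sites, the second is conditional on site. In a logistic model the gain comes mainly through this change and not through a smaller residual variance.

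**The case against.** The strongest case against is that omitting site is defensible here. One counselor serves both sites, counseling and surveys are by telephone, and the documents record no difference between the sites in procedure. Individual randomisation balances site in expectation, the ordinary confidence interval already allows for chance imbalance, and the simulated test holds its level without a site term. All of that stands. It is why the point is minor.

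Some stronger readings are tempting, and the documents do not support them.

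- *The sites recruit by different routes.* A reader might infer this from the pain table: "with the monthly pain recruitment table at West Haven and Newington". But flyers, provider referrals and "self-referrals from Clinicaltrials.gov at VACHS and VA Central Western Massachusetts Healthcare System (VACWM") are listed for both systems, and the administrative data pull is not limited to one. Only the table is tied to named locations, and the text does not say which system they belong to.
- *NRT access or saliva verification differs by site.* For NRT, the study will "contact the patient's PCP to facilitate a NRT prescription if the PCP agrees". That varies between physicians, including within a site, and no site difference is stated for NRT or for saliva collection.
- *Site confounds the comparison, or inflates the error term.* Randomisation rules out the first as a systematic effect. The second is linear-model reasoning, which applies to the pain outcomes but not to the primary logistic model.

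It can also be objected that the stratification list might be longer than gender, since the pain section uses the plural. The available text does not describe the randomisation method, and leading pages were removed before review, so no criticism is made of that. The parenthesis in the abstinence section nevertheless names gender alone, and the models are described in full without site.

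None of this argues against adding the covariate. It argues against calling its absence an error.

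**Conclusion.** The point holds as a minor improvement. Two health systems enrol, gender is the only stratification variable named, site is in no model, and the sole route to adjustment is optional and follows inspection of the data. The comparison is not biased and the type I error rate is sound.

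The size is a 95% range of ±7.4 points in the between-arm difference in VACWM share (±9.0 if 371 is the total). With a 10-point site difference, that shifts the abstinence difference by at most about 0.7 to 0.9 points at the 95% limit. The loss of power is about 0.6 to 2 points at an odds ratio of 2. These figures rest on assumed 1:1 allocation, assumed abstinence rates and assumed site differences. If the sites do not differ in abstinence, there is no shift to remove and no power to regain from adjusting for site.

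A reader might go further and conclude that allocation should be re-stratified by site. An effect of this size does not justify altering the allocation list at an unknown stage of enrollment.

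**What to change.** Before outcomes are examined by arm, amend the statistical section to:

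1. Include site (VACHS or VACWM) as a fixed covariate alongside gender in the Hypothesis 1.1/1.2 logistic and GEE models and in the Hypothesis 2.1 mixed model. List the covariates by name in each paragraph, so that the GEE description and the plural in the pain section are no longer open.
2. State that the odds ratio is then conditional on site, as it already is on gender.
3. Report the treatment effect by site descriptively, without a test. With 100 Veterans at VACWM, the standard error of the abstinence difference there is about √(0.10 × 0.90 × 4/100) = 6 points at an assumed 10% abstinence, too wide for inference.

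The cost is one degree of freedom per model and a few lines of text. No new data are needed, and the allocation list stays as it is. If the team prefers to leave site out, a sentence giving the reason would also close the point.

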## V. Outcomes:

Participants will be surveyed three times: enrollment, 6-months post-intervention and 12-months post-intervention using VA RED Cap to collect these data. Baseline survey will assess demographics, smoking history, nicotine dependence, global self-efficacy to quit smoking, depression, pain intensity and other covariates related to pain and smoking, via telephone. Follow-up surveys will be administered at 6-months and 12 months post-intervention. The follow-up surveys will assess smoking status, pain intensity, use of intervention materials (e.g., NRT, PASS activity booklet), and intervention acceptability (e.g., intervention appropriateness, suitability, effectiveness, and convenience). Participants will be compensated \$25 per completed follow-up survey. We will abide by the patient's preference since many patients may be reluctant to send their sensitive bank information or provide it over the phone for this telephone-based study.

Saliva samples will be collected from participants who report not smoking in the last 7 days (7-day point prevalence) in order to biochemically validate their self-reported smoking status. This process has been shown to improve the validity of self-reported smoking cessation. Samples will be collected at next clinic visit following the telephone interview. Saliva samples will measure cotinine levels using NicAlert dipsticks with a standard cut point of 16 ng/ml to determine abstinence. Participants will receive \$10 incentive for providing each saliva sample.

Counseling session fidelity will be assessed using audio-taped recordings of sessions. We aim to record approximately 20% of sessions (all sessions in the first 3 months of the study and then one week every 2 months for the remainder of the study). Investigators will rate 10% of the sessions to ensure protocol fidelity and lack of drift of information from the SMK-CBI to SMK-STD over time.

**Outcome 1: Prolonged abstinence:** In keeping with the SNRT recommendations for measuring abstinence, we will use prolonged abstinence as our main outcome and allow for a grace period around quit date. During the 6- and 12-month follow-ups, patients will be asked about prolonged abstinence, "In the past 6 months, have

you smoked at least a part of a cigarette on each of 7 consecutive days?" and "In the past 6 months, have you smoked any cigarettes in each of 2 consecutive weeks?"

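### The main abstinence model adjusts only for gender and leaves baseline smoking predictors to optional, imbalance-triggered analyses; the test is valid but gives up some power if those variables predict quitting

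*Combined protocol and SAP*

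**What the plan says.** Under Analyses, Hypotheses 1.1 and 1.2 (section VI), the primary comparison is set out as follows: "We will use logistic regression to test for a between-group difference in abstinence rates at 6 months". The displayed equation contains an intercept and the arm indicator, and the text then adds one covariate: "The model will also include stratification variables (gender) as recommended in the CPMP guidelines". The same approach serves prolonged and 7-day point prevalence abstinence. The result is reported as an odds ratio with a 95% CI. The paragraph on 12-month sustainability describes a GEE with a logit link and names no baseline covariate.

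Section V (Outcomes) shows what is known about each Veteran at enrolment: "Baseline survey will assess demographics, smoking history, nicotine dependence, global self-efficacy to quit smoking, depression, pain intensity and other covariates related to pain and smoking".

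The Data Summary paragraph of section VI deals with any other adjustment. The trigger is imbalance: "Evidence of imbalance in baseline characteristics will be noted and discussed as to whether they are clinically significant". The response is optional: "we will consider sensitivity analyses adjusting for these baseline characteristics to ensure that an observed intervention effect is not due to this baseline imbalance". No variable is named.

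**The concern.** In a logistic model, leaving out a baseline variable that predicts the outcome gives an arm log odds ratio closer to zero than the one conditional on that variable. It also weakens the test of no effect, even when the arms are perfectly balanced. Nicotine dependence and self-efficacy to quit are natural candidates. The plan's own third aim treats change in self-efficacy as a route to quitting, and the baseline value is measured at enrolment, so adjusting for it does not block that route.

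Imbalance is also a poor criterion for choosing covariates. It picks variables by chance difference between arms, not by their relation to quitting, and here it never reaches the main test. With no list fixed in advance, several adjusted results could be produced with no stated rule for which to report.

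Any lost power carries forward, because the mediation analysis under Hypothesis 3.1 is run only if the arm coefficient in the first Hypothesis 1.1 model is significant.

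**Working it through.** **Inputs from the documents.** The model is arm plus gender, as quoted. Section 6 (Research Plan) gives the recruitment goals: "The anticipated goal for this VACHS study is to recruit 371 veterans, and VACWM will look to recruit 100 Veterans". If the two are additive, N = 371 + 100 = 471; no total is stated. The documents give no alpha, power, abstinence rates, effect size, dropout or allocation ratio, so there is no figure of the plan's own to reproduce.

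**Assumptions (mine).** 1:1 allocation; two-sided Wald test at 5%; 20% women; gender unrelated to outcome. The baseline variables are represented by one score with standard deviation s on the logit scale, so the odds ratio per SD of the score is exp(s). Intercepts are solved so that the marginal abstinence rates equal the assumed ones.

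**First set.** N = 371 or 471 with no missing data; 8 vs 17%, 10 vs 20% and 15 vs 26%; 3,000 simulated trials per setting. Arm plus gender is compared with arm plus gender plus score. Power at 10 vs 20%:

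| Score OR per SD | s = ln(OR) | N=371: gender only → adjusted | N=471: gender only → adjusted |
|---|---|---|---|
| 1.3 | 0.26 | 77.4% → 77.9% | 87.0% → 87.4% |
| 1.5 | 0.41 | 76.9% → 77.7% | 87.1% → 88.1% |
| 2.0 | 0.69 | 77.3% → 79.1% | 85.8% → 87.5% |
| 2.5 | 0.92 | 77.0% → 81.2% | 86.8% → 89.9% |

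Over all three pairs of rates, the gain is about 0 to 1 point at OR per SD up to 1.5, about 2 to 3 points at 2.0 and about 3 to 6 points at 2.5. The simulation standard error of one power figure is about √(0.77 × 0.23 / 3000) = 0.008, or 0.8 points. Both models are fitted to the same simulated trials, so the differences are steadier than that.

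**Where the gain comes from.** At N = 371, 10 vs 20%, OR per SD 2.0, the mean log odds ratio moves from 0.824 to 0.879 and its standard error from 0.311 to 0.322. The ratio of estimate to standard error goes from 0.824/0.311 = 2.65 to 0.879/0.322 = 2.73. Squaring the quotient, (2.73/2.65)² ≈ 1.06, equivalent to about 6% more Veterans. The standard error rises by 0.322/0.311 − 1 = 3.5%, so the interval for the log odds ratio becomes wider.

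**Second set.** 10 vs 18%, 12 vs 22% and 15 vs 25%; N = 471, or 377 if 80% are observed (0.8 × 471 = 376.8); 4,000 trials per setting; same two models.

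| s | Power gain (points) | Excess variance of the rate difference without the score |
|---|---|---|
| 0.5 | about 1 to 2 | 3 to 4% |
| 0.8 | about 3 to 5 | 7 to 10% |
| 1.0 | about 4 to 6 | 11 to 16% |

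The last column refers to the standardised difference in abstinence rates. At s = 0.37 the gain is about 1 point. Example: 12 vs 22%, N = 471, s = 1.0 gives 83% → 87%. As a sample-size ratio this is [(1.96 + 1.126)/(1.96 + 0.954)]² = (3.086/2.914)² ≈ 1.12.

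**What two covariates would need.** If the two are independent and equally strong, s = √2 × ln(OR per SD of each). An odds ratio of 1.3 each gives √2 × 0.262 = 0.37. Reaching s = 0.5, 0.8 or 1.0 requires exp(s/√2) = 1.4, 1.8 or 2.0 each.

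**The case against.** The strongest reply is that nothing is broken. Treatment is randomised, the main model is fixed in advance, and the arm-plus-gender odds ratio is a valid, near-marginal quantity. A reader might infer from the attenuation that the planned estimate is biased. It is not: the conditional and near-marginal odds ratios differ because the odds ratio is non-collapsible, and no type I error problem follows.

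A reader might also expect adjustment to tighten the reported odds ratio. The calculation shows the reverse on the log scale. Precision improves only for a standardised rate difference, which the plan does not currently report.

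Nor do the documents support calling these variables strong predictors, since they report no association with abstinence. The larger gains need each of two independent covariates to carry an odds ratio of about 1.8 to 2.0 per SD. With weak predictors the gain is close to nothing. All of this stands.

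The Data Summary wording might also suggest that analysts could choose the headline result. They could not: imbalance-driven adjustment is labelled as sensitivity analysis and cannot replace the fixed main test. What remains is that the content of those sensitivity analyses is open.

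Finally, the Missing Data paragraph favours a parsimonious treatment-effect model. That remark explains the use of auxiliary variables in imputation. It does not rule out two covariates, and at roughly 15% abstinence 471 Veterans would give about 0.15 × 471 ≈ 70 quitters, enough to support them. The N = 377 case simply drops unobserved Veterans, whereas the plan intends multiple imputation, so it is only a rough lower case.

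**Conclusion.** The point holds as a modest weakness of efficiency and pre-specification. It is not an error in the main test, which is valid and unbiased as planned. If baseline nicotine dependence and self-efficacy predict quitting, the arm-plus-gender model gives up about 0 to 2 power points when they are weak to moderate together (s up to 0.5) and about 3 to 6 points when strong (s of 0.8 to 1.0). These figures rest on assumed abstinence rates, 1:1 allocation, N of 377 to 471 and an unknown prognostic strength. The direction is secure; the size is not. Because the remedy needs no new data, it is worth making even if the gain proves to be at the low end.

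**What to change.** In Analyses, Hypotheses 1.1 and 1.2, name baseline nicotine dependence and baseline global self-efficacy to quit, together with gender, as covariates in the 6-month logistic model and the 12-month GEE. Apply this to both abstinence outcomes, whatever balance is observed. State that the adjusted odds ratio is conditional on these covariates, and report beside it a standardised difference in abstinence rates (averaged over the covariates) with a 95% CI. Keep the arm-plus-gender model as the named sensitivity analysis. In Data Summary, replace the imbalance-triggered choice of covariates with this fixed list; describing baseline imbalance can stay.

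The cost is wording only, since both variables are already collected. The small downside is that the main odds ratio becomes a conditional estimand with a slightly larger standard error on the log scale, which is why the rate difference should sit next to it. The change should be made before outcome data are examined by arm.
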